#### 2. STUDY DESIGN and METHODS

#### A. Study Overview

We propose to assess the effect of Naloxegol on reversing opioid-related side effects in patients recovering from elective primary hip surgery under spinal anesthesia who will be randomly assigned to oral Naloxegol or placebo for two postoperative days or until the date of discharge, whichever occurs earlier (**Table 1**). The design will be a randomized, double-blind, placebo-controlled trial of oral Naloxegol in adults having elective primary hip or knee surgery under spinal anesthesia. The study will be performed at the Cleveland Clinic hospitals.

	Preopera tive visit	Morning of surgery	During surgery	PACU*	POD** 1	POD 2	Day of discharge	
Screening for eligibility	Х	Х						
Consenting	Х							
Baseline medical, demographics, Apfel score, Patient functionality and drug history	Х	х						
Pertinent blood studies (laboratory)	Х				Х	х		
AE/SAE collection		Х			Х	Х		
Study drug (in morning, 1 hr before or 2 hr after meal)		Х			х	х		
Bladder scan at least 2 hours after study drug (morning)					х	Х		
Bladder scan (evening)				Х	х	Х		
Intraoperative record data collection			Х					
Opioid–Related Symptom Distress Scale (ORSDS)					х	х	Х	
Opioid complications survey***				X	х	Х	х	
Numerical pain score				Х	Х	Х	Х	Х
Quality of recovery survey							Х	

Table 1: study flowchart.(Detailed information will be in the CRF's)

\* PACU = post-anesthesia care unit

\*\* POD = post-operative day

\*\*\* Opioid complications survey includes nausea, vomiting, itching, ileus, anti-emetic use, antipruritic use, anti-opioid use

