#### **Enrollment procedures**

The following events will occur in order:

- 1. Screening for eligible patients
- 2. Informed consent
- 3. Randomization

- 4. Administration of study drug starting the morning of surgery and for 2 additional mornings
- 5. Collection of data
- 6. Completion of CRF information

The treatment periods extends from the morning of surgery until the earlier of POD 2 or hospital discharge. Study personnel will follow the study subject until the earlier of POD 2 or hospital discharge. In the case of an adverse event, the study subject will be followed until the resolution of the event.

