#### F. Measurements

Data will be recorded on a case report form (CRF) which will be available electronically and on paper format.

Demographic data to be obtained includes height (cm), weight (kg), age (yr), gender, physical status (ASA), and self-declared ethnicity. Patients will be questioned for social history (tobacco) and medical history (pulmonary disease, kidney disease, diabetes mellitus, neurological disease, chronic pain conditions, illegal drug usage, alcohol abuse, myocardial infarction, previous surgery or stent placement and medications usage). Available preoperative laboratory tests and medication list will be recorded. Individual risk for nausea and vomiting will be determined using the Apfel score.

Data obtained from electronic medical records will include: operation time, surgery type, intraoperative opioid consumption, postoperative opioid consumption in PACU and in ward,

breakthrough pain medication requirements, pain scores in PACU and ward, requirement of oxygen in PACU and ward, nausea and vomiting, requirement of antiemetics, pruritus, requirement of antihistaminic medications, ambulation time, flatus, ileus, bowel movements, constipation, length of stay and any side effects or complications. Preoperative and postoperative laboratory data including but not limited to liver function and coagulations test results will also be collected from electronic medical records. Patient functionality will also be recorded including bathing, toileting, walking and moving.

The Residual volume will be measured within 30 minutes after urination using the batterypowered, portable Bladder scan™ BVI 3000® (Verathon, Bothell, WA, USA). The scanner will be placed on the suprapubic area and held stationary during measurement scanning. The diameter of the bladder and volume of urine will be calculated from the scan data. Scans will be repeated several times to ensure accuracy in measurements. The average of the measurements at each measurement time will be analyzed. All clinical procedures will be performed by trained MD research fellows in the ward twice daily. Surgical team will be blinded to volume determined by scanning and we will also record if they had ordered indwelling catheterization.

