#### Primary analysis.

We will test the primary hypothesis that subjects who received Naloxegol 25 mg given once in the morning every day will have lower volume of residual urine in bladder when compared to placebo. We will compare the randomized groups on the volume of residual urine in bladder, which will be measured twice per day for up to 3 days (i.e., a maximum of 6 measurement times in total), using a linear mixed model adjusting for the within-subject correlation (using an autoregressive correlation structure). At each measurement time, the average of the measurements will be analyzed. Any imbalanced baseline characteristics and volume of residual urine in bladder prior to the procedure will be included as covariates in the model. If the group-by-time interaction is non-significant (P > 0.20), we will assess the group difference on the volume of residual urine across over all the measurements. In the presence of a group-by-time interaction, the group difference will be assessed separately at each measurement time and a Bonferroni correction will be made for multiple comparisons to maintain the hypothesis-wise 2-sided type I error at 0.05 (the significance criterion will be 0.05 / 6).

Second, we will assess the treatment effect within chronic opioid users and nonusers using the same statistical methods as above. The significance level will be 0.025 for each of the two subgroup analyses (Bonferroni correction).

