#### H. Sample Size Considerations

The sample size consideration was based on the test for the primary hypothesis that patients who received Naloxegol 25 mg given once in the morning every day will have lower volume of residual urine in bladder when compared to placebo. We would need 62 patients per group [56] to have 90% power at a 2-sided alpha level of 0.05 to detect an effect size of 0.4 or more. The effect size estimation of 0.4 was very conservative as compared to the mean difference of 120 ml (SD: approximate 60 ml) in the volume of residual urine observed by Jose Carlos, I. T., et al [57]. The effect size is the difference in means of the two randomized groups divided by the pooled standard deviation. A maximum of six measurements are planned, twice per day for 3 days. However, we assumed 4 measurements per patients with a correlation of 0.3 to be conservative for the sample size calculation. Considering a loss of follow-up rate of 10%, we will need 12 more patients to reach the planned power with an end sample size of 136. A blinded data quality check will be conducted at 50% (68 patients) of the planned enrollment of 136 patients. In addition to the 136 patients, we will enroll 2 pilot patients to test feasibility of recruitment, protocol adherence, randomization process, and data collection.

SAS software version 9.4 for Windows (SAS Institute, Cary, NC) will be used for all statistical analyses and graphics.

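### The analysis text counts six residual-volume scan times and tests each at 0.05/6, but Table 1 schedules five, and no section says whether the PACU scan enters the primary contrast

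*Combined protocol and SAP*

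**What the plan says.** All references are to the combined protocol and SAP.

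- **Data Analysis, Primary analysis:** residual volume is "measured twice per day for up to 3 days (i.e., a maximum of 6 measurement times in total"). The main route is one contrast averaged over every scan: "If the group-by-time interaction is non-significant (P > 0.20), we will assess the group difference on the volume of residual urine across over all the" (last word of the sentence left out). If there is an interaction, groups are compared at each time, with the correction "to maintain the hypothesis-wise 2-sided type I error at 0.05 (the significance criterion will be 0.05 / 6"). The residual volume before the procedure is a covariate.
- **Sample Size Considerations (H):** "A maximum of six measurements are planned, twice per day for 3 days". The calculation itself assumes four measurements with correlation 0.3, described as conservative.
- **Study Overview, Table 1 (as extracted):** the row "Bladder scan at least 2 hours after study drug (morning") is marked on POD 1 and POD 2. The row "Bladder scan (evening") is marked in PACU, on POD 1 and on POD 2. That makes five scans. No preoperative scan is marked.
- **Measurements (F):** "All clinical procedures will be performed by trained MD research fellows in the ward twice daily". No days and no total are given.
- **Enrollment procedures:** "The treatment periods extends from the morning of surgery until the earlier of POD 2 or hospital discharge". Study follow-up ends at the same point, apart from follow-up of adverse events.

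**The concern.** The number and identity of the scan times decide two things in the primary analysis.

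The first is the by-time threshold. A divisor of six presumes six tests. If five are scheduled, a p-value between 0.0083 and 0.010 would be declared non-significant although the error rate the plan sets for itself permits rejection.

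The second is the averaged contrast. It runs over all measurements, but no section lists them or says whether the PACU value is one of them. The same list fixes the degrees of freedom of the interaction test that selects the branch (number of times minus one: 4 with five times, 3 with four). If the list is settled only after unblinded data are seen, the primary result could depend on that choice.

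**Working it through.** **Inputs.** From section H: 62 per group, two-sided alpha 0.05, power 90%, effect size d = 0.4, four measurements, correlation 0.3. From Primary analysis: threshold 0.05/6. From Table 1: five post-dose scans. Normal approximations are used throughout.

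**1. Counting the times.** The study window covers three calendar days: day of surgery, POD 1 and POD 2. Twice daily gives 3 × 2 = 6. Table 1 gives 1 (PACU) + 2 (POD 1) + 2 (POD 2) = 5. The sixth would have to be a second post-dose scan on the day of surgery, which no section schedules. It cannot come after POD 2, because follow-up has ended. It cannot be the pre-procedure volume, which is a covariate.

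**2. Reproducing the plan's sample size.** For a mean of m measurements with exchangeable correlation ρ, the variance factor is v = (1 + (m − 1)ρ)/m, and n per group = 2((1.960 + 1.282)/d)² × v.
- m = 4, ρ = 0.3: v = 1.9/4 = 0.475.
- n = 131.34 × 0.475 = 62.4, against 62 stated. Power at 62 is 89.8%.

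The stated figure therefore reproduces under exchangeable correlation, which is kept below. Under a first-order autoregressive structure with ρ = 0.3, v would be 0.388 and n would be 52.

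**3. By-time threshold.** If k times are tested at 0.05/6, the Bonferroni bound on the familywise error is k × 0.05/6. Single-time power is Φ(0.4√(62/2) − z), where 0.4√31 = 2.227.

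| Times tested | Bound if 0.05/6 is kept | Matching threshold | Critical z | Single-time power at the matching threshold |
|---|---|---|---|---|
| 6 | 0.050 | 0.0083 | 2.638 | 34.1% |
| 5 (Table 1) | 0.042 | 0.0100 | 2.576 | 36.4% |
| 4 (without PACU) | 0.033 | 0.0125 | 2.498 | 39.3% |

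Keeping 0.05/6 with five times costs 36.4 − 34.1 = 2.3 percentage points at a single time. With four times it costs 39.3 − 34.1 = 5.2 points.

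**4. Averaged contrast.** Power = Φ(δ√(31/v) − 1.960), where δ is the mean effect over the scans included. The effect is taken as 0.4 at each POD 1 and POD 2 scan. The PACU effect is an assumption, shown as a range, because the documents give no figure for it.

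| Scans averaged | Assumed PACU effect | δ | v | Power |
|---|---|---|---|---|
| 4 (POD 1 and 2) | not included | 0.40 | 0.475 | 89.8% |
| 5 | 0.4 (full) | (4 × 0.4 + 0.4)/5 = 0.40 | 0.44 | 91.9% |
| 5 | 0.2 (half) | (4 × 0.4 + 0.2)/5 = 0.36 | 0.44 | 85.6% |
| 5 | 0 (nil) | (4 × 0.4)/5 = 0.32 | 0.44 | 76.6% |

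If the effect is constant over time, adding the PACU scan leaves the averaged effect unchanged and raises power.

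**The case against.** The strongest reply is that six is stated as a maximum. Dividing by a maximum keeps the familywise error at or below 0.05 whether four, five or six times are tested, so the test is valid and only mildly conservative, and only in the interaction branch. This stands. A reader might infer that 0.05/6 is an erroneous threshold; the arithmetic does not support that. What remains is that a patient who stays for the whole schedule in Table 1 has five scans, so six is not reached even as a maximum.

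A reader might also take the Measurements section as a third definition, ward scans only and therefore four. That sentence says who does the procedures, where and how often. It gives no count and does not expressly exclude PACU. Twice daily over three calendar days would agree with six. The conflict is between the analysis and sample size text on one side and Table 1 on the other.

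Third, Table 1 refers to the case report forms for detail, and these are not available here. The extracted table also has an unlabelled last column, so the marks should be checked against the PDF. In the same table, however, the study-drug marks fall on the morning of surgery, POD 1 and POD 2, as the text requires, which suggests that the columns are aligned. The summary of changes also mentions PACU and evening scans; nothing here relies on it.

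Finally, it is tempting to say that the PACU scan dilutes the primary effect because of spinal anesthesia. The documents do not show this. Spinal or general anesthesia is allowed with no stated proportions, the first dose precedes surgery so the PACU scan is on treatment, and no figure is given for the effect there.

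**Conclusion.** The inconsistency is real and touches the primary analysis, but its established size is small. Under Table 1, the by-time threshold is stricter than the plan's own 0.05 requires: familywise error at most 0.042, and about 34% instead of 36% power at a single time, given d = 0.4 and 62 per group. Type I error is controlled. The sample size reproduces, and under a constant effect five scans give it more power, not less.

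The more important gap is that the set of scans in the averaged contrast is not fixed. Its consequence depends on an unknown PACU effect: relative to 89.8% on the four POD 1 and 2 scans, power could be 2.1 points higher or 13.2 points lower over the range shown. These powers assume exchangeable correlation of 0.3 and complete scans. They show why the list should be fixed in advance. They do not show that including PACU does harm, nor that it should be dropped.

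**What to change.** Before unblinding:

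1. List the scheduled post-dose scan times once, and state whether the PACU scan is in the primary model.
2. Make Table 1, Measurements, Primary analysis and Sample Size Considerations agree with that list.
3. Set the Bonferroni divisor to the length of the list: 0.05/5 under Table 1 as it stands, 0.05/4 if PACU is excluded, and 0.05/6 only if a second post-dose scan on the day of surgery is actually scheduled.

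This costs wording only. Whether PACU counts is for the sponsor to decide, and exclusion has a price. Four scans would then be the maximum, so the sample size assumption of four would no longer be conservative. Scanning also ends at discharge, and the Protocol section (E) omits a subsequent scan after catheterization. By the formula in step 4 with d = 0.4, power at 62 per group is 89.8% with four scans per patient, 86.2% with three (v = 1.6/3 = 0.533) and 78.9% with two (v = 1.3/2 = 0.65). Using the interaction test to choose the branch is a separate matter that this change does not address.

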#### E. Protocol

Patients must meet all inclusion and exclusion criteria to be eligible for the study. After eligibility is confirmed, patients will receive complete information about the study both verbally and in writing. Informed consent must be obtained from the patients prior to randomization and study-specific procedures.

Anesthetic management will follow pre-established clinical and institutional guidelines. Patients can be pre-medicated and will receive spinal or general anesthesia per institutional routine according to attending anesthesiologist discretion. Spinal anesthesia will include the standard monitoring for the given operation, and will occur after the electrocardiogram and monitoring equipment are placed on the patient. Prophylactic antibiotics will be given per surgical routine. During the induction of general anesthesia, indwelling urinary catheters will be inserted only in the patients with operation time exceeding 3 h or who required meticulous monitoring of the intraoperative fluid status. Intraoperative and postoperative fluid management will be left to discretion of the clinicians, who will be administrating them using institution standards.

Randomization (1:1) will be web-based and initiated prior to conclusion of surgery; allocation will thus be concealed from investigators. Randomization will be stratified based on chronic opioid use (if present) to ensure balance between treatment groups within chronic opioid users and nonusers. Chronic opioid use will be defined as opioid use for more than 30 consecutive days, at a daily dose of 15 mg or more of morphine or equivalent, within the 3 months before surgery. The treatment groups will be oral Naloxegol and placebo.

Naloxegol or placebo will be administered starting the first morning of surgery and continued for two postoperative days or until hospital discharge (whichever occurs first) with 25 mg (or equivalent size and shape of Placebo). The post-operative study drug doses will be given in the morning 1 hour before or 2 hours after the morning meal. Intraoperative and postoperative pain medications will be left to discretion of the anesthesiologist.

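### Separate 0.025 tests in chronic opioid users and nonusers, without a treatment-by-chronic-use interaction, cannot show whether the effect on residual volume differs between the strata

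*Combined protocol and SAP*

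**What the plan says.** Section E (Protocol) makes chronic opioid use the stratification factor: "Randomization will be stratified based on chronic opioid use (if present) to ensure balance between treatment groups within chronic opioid users and nonusers". The expected share of users is not given. Allocation is 1:1.

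Section G (Data Analysis, Primary analysis) first describes the overall comparison by linear mixed model. As a second step, "we will assess the treatment effect within chronic opioid users and nonusers using the same statistical methods as above". The threshold for this step is set out next: "The significance level will be 0.025 for each of the two subgroup analyses (Bonferroni correction").

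The only interaction in the analysis plan is treatment by time: "If the group-by-time interaction is non-significant (P > 0.20), we will assess the group difference" across all measurements. No treatment-by-chronic-use term appears, and there is no rule for comparing the two subgroup results.

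Section H (Sample Size Considerations) sizes the overall comparison only: "We would need 62 patients per group [56] to have 90% power at a 2-sided alpha level of 0.05". The planning effect is 0.4 SD, with 4 measurements per patient and correlation 0.3. No subgroup power is given.

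**The concern.** Two within-stratum tests ask whether the effect is zero in users and whether it is zero in nonusers. Neither asks whether the two effects are equal. If the strata differ in size, the larger can reach 0.025 and the smaller miss it although the drug acts identically in both. The Bonferroni correction limits false positives across the two tests but does nothing about this false contrast.

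The tests stand under the primary analysis and use the randomisation stratum, so a split result would be prominent. The risk is a statement that the drug works in one type of patient and not the other, when the data show no such difference.

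**Working it through.** **Inputs.** From section H: effect d = 0.4 SD, 62 evaluable per arm, two-sided 0.05, 90% power, m = 4 measurements, correlation 0.3. From section G: two-sided 0.025 per stratum, so the critical value is 2.241. The user share s is an assumption, varied from 10% to 50%.

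**Reproducing the plan's figure.** With equal correlation between measurements, the variance factor for a patient's mean is f = (1 + 3 × 0.3)/4 = 0.475. Then n per arm = 2 × 0.475 × (1.960 + 1.282)²/0.4² = 62.4, and power at 62 is 0.898. The stated 62 is reproduced to within rounding.

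**Power per stratum.** The standard error is √(2f/n), with n = 62s per arm for users and 62(1 − s) for nonusers. Power is Φ(d/SE − 2.241), plus a negligible opposite tail.

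Example at s = 20%:
- Users: n = 12.4, SE = √(0.95/12.4) = 0.277, d/SE = 1.445, power 21%.
- Nonusers: n = 49.6, SE = √(0.95/49.6) = 0.138, d/SE = 2.890, power 74%.

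The strata are independent. With powers a (users) and b (nonusers), P(exactly one significant) = a(1 − b) + b(1 − a) = 0.213 × 0.258 + 0.742 × 0.787 = 0.055 + 0.584 = 0.64. Of this, 58 points are significance in nonusers only.

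**Uniform effect of 0.4 SD:**

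| User share | Power, users | Power, nonusers | Exactly one | Nonusers only | Both | Neither |
|---|---|---|---|---|---|---|
| 10% | 11% | 80% | 73% | 71% | 9% | 18% |
| 20% | 21% | 74% | 64% | 58% | 16% | 20% |
| 30% | 32% | 68% | 57% | 46% | 22% | 22% |
| 40% | 42% | 60% | 52% | 35% | 25% | 23% |
| 50% | 52% | 52% | 50% | 25% | 27% | 23% |

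Among trials with a significant overall test, exactly one stratum is significant in 81% to 54% (share 10% to 50%, by simulation).

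**Other uniform effects.** P(exactly one) for shares of 10% to 50%:

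| True effect | Exactly one stratum significant |
|---|---|
| 0.2 SD | 26% to 24% (neither: 73% to 75%) |
| 0.3 SD | 52% to 42% |
| 0.4 SD | 73% to 50% |
| 0.5 SD | 80% to 39% |
| 0.6 SD | 76% to 21% |
| 0.8 SD | 58% to 2% |
| 2.0 SD (cited study, 120 ml / 60 ml) | 0.2% or less (both: 99.8% or more) |

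**What the interaction would add.** Under a uniform 0.4 SD effect with exactly one stratum significant, an interaction test at 0.05 is non-significant in 95% to 90% of cases (share 10% to 50%, by simulation). At s = 20% its standard error is √(0.277² + 0.138²) = 0.31. Power for a difference of 0.4 SD (effect in one stratum, none in the other) is then about 25%; over shares of 10% to 50% it is 16% to 37%.

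**Joint false-positive chance.** With no effect, the chance that the overall test at 0.05 or either stratum test at 0.025 is significant is about 7.5% to 7.8% (share 10% to 50%, by simulation).

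**Sensitivity.** The planned model uses an autoregressive structure, whereas the sample size reproduces under equal correlation. With autoregressive correlation 0.3, the range for exactly one at 0.4 SD is 78% to 47%. If the treatment-by-time rule triggers within a stratum, the per-time tests are stricter and none of these subgroup figures apply.

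**The case against.** The strongest defence is that the subgroup tests are prespecified, few, based on the randomisation stratum and Bonferroni-corrected. The plan asks only for the effect within each stratum and nowhere says that the two results will be contrasted. That stands: the false contrast is a risk of later interpretation, not a planned conclusion. But the plan offers no other basis for interpreting a split result.

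A reader might infer four stronger things that the documents do not support.

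- *A uniform drug effect will usually look like an effect in one stratum.* This holds near the design effect, not in general. Section H calls 0.4 very conservative beside the cited study, and at 2.0 SD both strata are almost always significant. At 0.2 SD neither usually is.
- *The expected result is an effect in nonusers only.* That pattern is a majority at 0.4 SD only if users are about a quarter of patients or fewer. At an even split, users only is equally likely.
- *The plan breaks its own type I error promise.* It does not. The 0.05 in section G is hypothesis-wise and refers to the per-time comparisons within the primary hypothesis. The subgroup pair has its own correction. The 7.5% to 7.8% belongs to a wider family that the plan never undertook to control.
- *The stratum tests must be dropped.* The gap does not require it. The interaction test has low power and would often miss a real difference, so it supplements the stratum results.

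**Conclusion.** The point holds as an omission with a limited consequence. The plan stratifies on chronic opioid use and tests within each stratum, but has no analysis that can say whether the effect differs by that factor. At the plan's own 0.4 SD, a uniform effect gives significance in exactly one stratum in about 73% to 50% of trials for user shares of 10% to 50%, and this is the most likely single outcome at every share examined. The figures rest on the assumed share, a true effect near 0.4 SD, 62 evaluable per arm and equal correlation of 0.3 over 4 measurements. The omission itself rests on none of these. Only the subgroup interpretation is affected.

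**What to change.** For the subgroup step, add chronic opioid use and a treatment-by-chronic-use term to the primary mixed model. Report the interaction estimate with its 95% confidence interval and p-value, and both stratum effects with 95% confidence intervals from that same model. State that any claim of a different effect by chronic use will rest on the interaction, not on comparing the two 0.025 results. Label the stratum results as supportive of the overall test, given the joint false-positive chance shown above.

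The cost is a few lines of analysis plan and one extra model term beyond the stratum itself, which is already recorded for randomisation. No further patients or data are needed. The drawback is the interaction's low power: a non-significant interaction must not be read as proof that the effect is the same in both strata, and the confidence interval should carry the message.
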